10.2.9 Pain

Subjects experiencing pain due to hu14.18-IL2 will be treated with morphine or similar analgesics as needed and have their pain graded according to the CTCAE. It is recommended to have morphine available, but not given as a premed, on the first day of treatment. If pain is noted and morphine is needed on that first day, then including morphine as a premed for all subsequent doses may be helpful. Subjects with pain that is not controlled with IV narcotics or that requires IV narcotics > 48 hours after completion of hu14.18-IL2 on day 3 of any treatment course will not receive additional protocol treatment at that dose. Provided that the pain resolves, and eligibility requirements are met, subsequent courses would be given at $\frac{1}{2}$ the prior dose.

10.2.10 Nephrotoxicity

High dose IL2 is associated with nephrotoxicity, but this has been minor in subjects receiving IL2 doses similar to those to be administered in this study. Adequate renal function is an eligibility requirement. If renal function is worsening (ie: > 2 times the upper limits of normal but not yet Grade 3), nephrotoxic drugs (including indomethacin) should be avoided.

10.2.11 Infusional reactions

Hu14.18-IL2 will be held for any infusional reactions requiring additional supportive anti-allergic (non-steroidal) treatments (i.e., Benadryl, epinephrine) and will not be restarted until that toxicity resolves. Then, hu14.18-IL2 will be restarted at 100% dose. Patients who experience Grade 3 allergic reactions that are considered true allergic reactions (i.e., IgE-mediated and usually worsen with re-exposure) will not be retreated.

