5.3 Treatment schedule and dose

The treatment regimens for each study group are summarized below (see also Schema above):

- **Group A:** one course of IC, followed by surgical resection, followed by two courses of IC
- **Group B:** surgical resection, followed by three courses of IC

Guidelines for initiation of therapy, following the surgical resection (Course 1 for subjects randomized to Group B and Course 2 for subjects randomized Group A) are provided in Section 5.2. Treatment Courses 1-3 (for Group B) and Courses 2-3 (for Group A) will be repeated every 28 days (+/- 7 days to allow for scheduling constraints) at the same dose, provided that there is no dose limiting toxicity (see Section 5.4) or non-DLT toxicity the treating physician feels warrants dose reduction. Subjects can receive a maximum of 3 courses of therapy. Hu14.18-IL2 will be given on days 1, 2, and 3 of each course of therapy as a 4-hour continuous IV infusion at a daily dose of 6 mg/m²/d. (Note: given the relatively short supply of hu14.18-IL2 available, before each subject begins study treatment, we will confirm with the hospital pharmacy that there is sufficient material available in our pharmacy for that subject to receive all planned doses.) The infusions will be stopped only under the following circumstances: if dose-limiting toxicity is noted (see Section 5.4.4), if the treating physician deems it in the subject’s best interest to discontinue the infusion for a significant, but non-DLT toxicity, when blood draws are needed, when other intravenous medications must be administered, if adequate intravenous access is lost (and a new IV must be placed), and/or if a subject decides to withdraw from the study.

5.3.1 Subsequent Courses:

5.3.1.1 Subjects may continue treatment if all toxicities have recovered to \leq Grade 1 or the subject meets initial eligibility criteria, and there is no symptomatic disease progression (Section 6.0)

5.3.1.2 Course 3 will be administered only to subjects with a documented complete clinical response (i.e., no radiological or clinical evidence of disease) following Course 2 of treatment (see details regarding statistical evaluation in Section 9.5) provided that all toxicity has resolved to \leq Grade 1 or meets initial eligibility criteria.

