5.4 Dose limiting toxicity and subsequent courses at reduced dose

5.4.1 Definition of DLT

The definition of DLT in this study differs from the standard definition. Dose-limiting toxicity (DLT) will be defined as Grade 3 or 4 toxicity, using the NCI Common Terminology Criteria for Adverse Events (CTCAE), version 3.0, EXCEPT as detailed below in Section 5.4.3. These toxicities will be evaluated for all subjects beginning on Course 1 day 1 during all courses of this study except for the time from the initiation of the surgical resection until recovery from surgery and initiation of Course 1 (for Group B) or Course 2 (for Group A) of protocol treatment.

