5.4.3 Detailed listing of DLT exceptions

The following toxicities will be graded and recorded, but will not be used as criteria for determining DLT:

- a) Grade 3 pain, requiring intravenous narcotics, provided that the narcotics are controlling the pain, and that IV narcotics for pain are not required > 48 hours after completion of hu14.18-IL2 on Day 3 of any treatment course;
- b) Grade 3 nausea and vomiting that resolves within 48 hours after completion of hu14.18-IL2 on Day 3 of any treatment course;
- c) Grade 3 fever (i.e., T > 40° C) lasting < 6 hours and controllable with antipyretics;
- d) Grade 3 skin toxicity that improves with treatment (e.g., IV Benadryl) within 24 hrs;
- e) Grade 3 metabolic/laboratory toxicity of hyponatremia, hyperglycemia, or hypophosphatemia in the absence of CNS symptoms and/or sequelae, that improves with or without treatment within 48 hrs;
- f) Grade 3 sensory or motor peripheral (non-cranial) neuropathy (i.e., interference with function plus objective weakness) if transient and reversing within 3 days of completion of hu14.18-IL2 of any treatment course. Subjective findings (e.g., tingling, hot/cold hands) are expected and will not be DLT;
- g) Grade 3 hematologic toxicity (or grade 4 lymphopenia – a known transient marker of immune activation by IL2) which improves to at least Grade 2 or pre-therapy baseline values without requiring transfusion within one week of completion of hu14.18-IL2 of any treatment course (see Section 10.2.1 for management of hematologic toxicity and transfusion guidelines);
- h) Grade 3 infusional reactions lasting less than 24 hours, readily controlled with supportive (non-steroidal) treatments (i.e., Benadryl) and not requiring epinephrine;
- i) Grade 3 fatigue or ECOG performance status that resolves in ≤ 1 week;
- j) Grade 3 infection that resolves in ≤ 1 week.

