The above dose limiting toxicity exceptions are based on the known, published, transient, reversible toxicities of IL2 and hu14.18. These toxicities may be expected, based on observations of hu14.18-IL2 given to 33 + 14 (phase I and II respectively) adults with melanoma, administered by the same schedule at similar doses to that being tested in this trial, and will not require interruption, modification, or discontinuation of treatment. In our experience with hu14.18-IL2 in adults with melanoma, asymptomatic hypophosphatemia is a relatively frequent occurrence. Therefore, all subjects scheduled to receive this agent will be given oral phosphate supplementation prophylactically starting on day 1 and ending on day 8 of each course (see Section 10.3.4.3 for details). **All grade 4 toxicities (except for transient lymphopenia) are considered as DLT and require stopping treatment with hu14.18-IL2. Following resolution of a DLT, and if subsequent hu14.18-IL2 treatment is given, it must be given at a reduced dose.**

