5.4.4 Treatment cessation/dose modification for DLT or significant non-DLT toxicity

Any subject demonstrating DLT or significant non-DLT toxicity (see Section 10.1.2) will require that treatment with the study agents be stopped. Depending upon the nature of the toxicity and its resolution, subjects will be considered for continued treatment at a reduced dose as described below (see also Figure 1). Any planned drug administration that is withheld due to DLT will not be given on a delayed schedule to “make up” for missed drug. All dose modifications are permanent.

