5.4.4.1 Dose-reduction plan for hu14.18-IL2

For toxicity associated with hu14.18-IL2, there must also be consideration of the schedule of administration. If this toxicity occurs on day 1 or 2 of any course, treatment can be resumed during that same course (i.e., on day 2 or 3) at 50% of the starting dose only if the toxicity has improved to meet eligibility criteria in time to give the day 2 or day 3 dose on schedule. If eligibility criteria are not met in time to receive additional therapy during the course in which the toxicity occurred, but are met in time to start the next course (i.e., day 1 of the next course +/- 7 days), treatment will resume at 50% of the dose that caused the DLT. If toxicity again requires treatment cessation, treatment can be restarted at 25% of initial treatment dose. If treatment at this reduced dose results in recurrence of DLT or significant non-DLT toxicity, treatment will be permanently discontinued.

Repeat lab testing will be done weekly until eligibility criteria are met, and treatment will begin at 50% of the prior dose. If after 4 additional weeks of testing, eligibility criteria still are not met, the subject will not be eligible for any additional treatment with the study agent responsible.

Subjects with Grade 4 toxicity related to protocol treatment (other than transient lymphopenia from hu14.18-IL2, see Section 5.3.3.g) will not receive additional protocol treatment during that treatment course. Patients experiencing Grade 4 neutropenia or leukopenia that lasts \leq 4 days; Grade 4 thrombocytopenia that can be corrected with platelet transfusion (see Section 10.2.1); or Grade 4 nausea, vomiting, anorexia or fatigue lasting less than 2 days, and resolves to meet eligibility criteria, may be eligible to receive continued study therapy (provided that all other criteria for continued treatment are met) at 50% of the dose received prior to the onset of this toxicity. Subjects with any other Grade 4 toxicity related to the protocol treatment will not receive additional protocol treatment during that course and will be withdrawn from the study. Subjects experiencing Grade 4 events that are clearly unrelated to the study treatment, last \leq 3 days, and improve to meet eligibility criteria, may be eligible to receive continued study therapy (provided that all other criteria for continued treatment are met) at 50% of the daily dose received prior to the onset of this toxicity.

[figure not shown]

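### A Grade 3 infusional reaction that counts as a DLT restarts at full dose under 10.2.11 but at half dose, after FDA contact, under the DLT rules

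*Combined protocol and SAP*

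**What the plan says.** **The infusional-reaction rule.** Section 10.2.11 holds hu14.18-IL2 for any infusional reaction needing additional non-steroidal anti-allergic treatment, with Benadryl and epinephrine as its examples. Once the reaction has resolved, "Then, hu14.18-IL2 will be restarted at 100% dose". The only exclusion is for Grade 3 reactions judged to be true (IgE-mediated) allergy, which are not retreated.

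**The DLT rules.** Section 5.4.1 states: "Dose-limiting toxicity (DLT) will be defined as Grade 3 or 4 toxicity", apart from the exceptions in 5.4.3. Exception (h) reads: "Grade 3 infusional reactions lasting less than 24 hours, readily controlled with supportive (non-steroidal) treatments (i.e., Benadryl) and not requiring epinephrine". The text closing 5.4.3 adds: "Following resolution of a DLT, and if subsequent hu14.18-IL2 treatment is given, it must be given at a reduced dose". Section 5.4.4 says "All dose modifications are permanent". For a toxicity on day 1 or 2, section 5.4.4.1 says "treatment can be resumed during that same course (i.e., on day 2 or 3) at 50% of the starting dose", if eligibility criteria are met in time. If treatment resumes only at the next course, the dose is 50% of the one that caused the DLT. Footnote 4 to Figure 1 gives the steps: 50% after the first DLT, 25% after the second, stop after the third. Section 10.1.1 repeats the 50% rule and requires case-by-case FDA contact before resuming at a reduced dose after any DLT. Section 5.3 keeps the dose unchanged between courses only where there has been no DLT.

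**The concern.** The two sets of instructions overlap on one kind of event and give different doses for it. Section 10.2.11 has no exception for DLTs and no reference to 10.1, and it names the drug whose use takes a Grade 3 reaction outside exception (h).

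A physician managing a reaction is likely to turn to the section on infusional reactions. Followed as written, it gives the full dose again after a DLT and says nothing of FDA contact. A physician who starts from section 5.4 or 10.1.1 would halve the dose and call the FDA first. What is at stake is patient safety and consistent dosing, not the analysis.

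**Working it through.** There is no power or alpha figure to reproduce. The check compares the texts and then does some simple dose and frequency arithmetic.

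**Step 1: which events fall under both rules?**

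| Infusional reaction | DLT? | Section 10.2.11 | DLT and other rules | Conflict? |
|---|---|---|---|---|
| Grade 1–2 | No | 100% | No reduction required | No |
| Grade 3 meeting 5.4.3(h) | No | 100% | No reduction required | No |
| Grade 3, judged IgE-mediated | Yes, if it fails (h) | Not retreated | Reduced dose only if retreated | No |
| Grade 3, corticosteroids given | Yes, if it fails (h) | Non-steroidal treatment only | Withdrawn from protocol therapy (10.3.3.5) | No |
| Grade 3, not IgE-mediated, no steroids, needing epinephrine or lasting 24 hours or more | Yes | 100% | 50% at first occurrence, FDA contact | **Yes** |
| Grade 4, treatment-related | Yes | 100% if read literally | "will not receive additional protocol treatment during that course and will be withdrawn from the study" (5.4.4.1) | Wording gap only |

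The 24-hour case falls under 10.2.11 only if anti-allergic treatment was needed. A Grade 3 reaction that is not readily controlled also fails (h).

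**Step 2: dose difference.** Starting dose 6 mg/m²/d (5.3); steps from footnote 4.

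- First DLT: 6 × 0.50 = 3, against 6 mg/m²/d.
- Second: 6 × 0.25 = 1.5, against 6.
- Third: no treatment, against 6.

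Planned doses are 3 courses × 3 days = 9. Because the reduction is permanent:

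- Reaction on course 1 day 1, resolved in time: 2 + 3 + 3 = 8 doses remain. 8 × 6 = 48 against 8 × 3 = 24 mg/m².
- Resuming only at course 2: 6 doses remain. 6 × 6 = 36 against 6 × 3 = 18 mg/m².

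**Step 3: how often?** The documents give no rate for epinephrine-requiring reactions. The nearest proxy is the severe allergic reaction row of Table 2 (section 1.3.5), which shows none. The course 1 denominators sum to 3 + 6 + 6 + 6 + 6 + 6 = 33. With zero events in n, the one-sided 95% upper bound is 1 − 0.05^(1/n).

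- Phase I, n = 33: 1 − 0.05^(1/33) = 0.0868.
- Adding the 14 Phase II patients, reported with no protocol-defined DLTs, n = 47: 1 − 0.05^(1/47) = 0.0618. This assumes that Phase II used a comparable DLT definition.

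With up to 20 subjects accrued (9.3.2), these bounds correspond to 20 × 0.0868 = 1.7 and 20 × 0.0618 = 1.2 proxy events. They are upper limits, not estimates. The table below adds assumed rates, and an assumed 25–75% of such reactions that are retreatable (not IgE-mediated, no steroids).

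| Rate | Expected in 20 | Expected in conflict (25–75%) |
|---|---|---|
| 0.5% (assumed) | 0.1 | 0.025–0.075 |
| 1% (assumed) | 0.2 | 0.05–0.15 |
| 3% (assumed) | 0.6 | 0.15–0.45 |
| 6.2% (upper bound) | 1.2 | 0.31–0.93 |
| 8.7% (upper bound) | 1.7 | 0.43–1.30 |

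**Step 4: comparison within 10.2.** Nine subsections state a restart dose: 10.2.2, 10.2.3.2.2, 10.2.3.4, 10.2.4, 10.2.6, 10.2.7, 10.2.8, 10.2.9 and 10.2.11. Eight use 50%, although 10.2.3.4 (dyspnea) allows 100% where recovery took under an hour. Only 10.2.11 restarts every retreated event at full dose.

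**The case against.** The best defence is that the general rule settles the matter. The reduction after a DLT is mandatory and universal, and dose modification belongs to 5.4 and 10.1, whereas 10.2.11 sits under supportive care. On that reading 10.2.11 governs only the commoner, non-DLT reactions. This is a sensible guess at the intent, but the text does not say it. It also fits poorly with the mention of epinephrine, and with the IgE exclusion, which shows that Grade 3 events are within the section's scope. No visible text sets precedence. Figure 1 itself could not be read, but its surviving footnotes support the 50% step and the FDA's role.

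Several narrower objections stand:

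- On FDA contact, 10.2.11 is silent rather than contradictory; 10.1.1 still applies to any DLT.
- A missing reference to 10.1 does not single out 10.2.11. Of the nine subsections, only 10.2.3.2.2 has one (10.2.3.3 also does, but states no restart dose).
- Section 10.2.3.4 may raise a similar question. It permits full dose after brief desaturation, 5.4.3 lists no hypoxia exception, and Phase I counted hypoxia as a DLT.
- The second- and third-occurrence contrasts are less secure, because a recurring reaction may well be judged allergic and not retreated.
- The frequency ranges rest on assumed rates and shares.

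None of these removes the first-occurrence conflict.

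**Conclusion.** The concern holds. For a Grade 3 infusional reaction that fails exception (h), is not judged IgE-mediated and is not treated with steroids, the protocol gives two restart doses that differ twofold. This is an error in the text as written, not a missing detail.

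The dose contrast at first occurrence follows directly from the protocol. The frequency rests on a proxy event and assumed shares; on any of them, few if any of the 20 subjects would be affected. The primary endpoints and sample size do not change, and a Grade 3 case does not enter the Grade 4 stopping rules in 9.4.9. It should be corrected because it concerns re-exposure after a dose-limiting reaction and the correction is trivial.

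**What to change.** In 10.2.11, extend the restart sentence to read: "Then, hu14.18-IL2 will be restarted at 100% dose", *unless the reaction is a DLT under 5.4.1 and 5.4.3 (Grade 4, or Grade 3 not meeting 5.4.3(h)), in which case follow 5.4.4.1 and 10.1.1*. In the sentence after it, change Grade 3 to Grade 3 or 4, which closes the Grade 4 wording gap.

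Optionally, align the reporting exemption in 14.3.9, which also names epinephrine. Limit it to Grade 1–2 infusional reactions that are readily controlled with non-steroidal anti-allergic treatment, and Grade 3 reactions that meet 5.4.3(h).

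The cost is one clause and one word change in 10.2.11, with no effect on sample size, assessments or analysis.

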10.2.12 Surgical wound care

Should any subject in any of the treatment groups develop complications related to their surgical wound(s) (e.g., dehiscence, infection, etc.), a General Surgery consult will be obtained (preferably from the surgeon who performed that subject's resection) to manage such complications appropriately.

10.3 Concomitant Therapy

10.3.1 No other anti-neoplastic agents or growth factors can be used.

Radiotherapy may be given to surgical sites with close or microscopically positive surgical margins. Radiotherapy to these sites will be planned to occur immediately upon completion of all protocol therapy.

10.3.2 Prohibited medications: therapeutic anticoagulation with Vitamin K antagonists (e.g., coumadin); therapeutic-dose anticoagulation with heparin, resulting in a prolonged PTT; or therapeutic-dose anticoagulation with low molecular weight heparin (i.e., at doses that usually decrease Factor Xa). Low (prophylactic) dose low molecular weight heparin or coumadin (i.e., 1 mg/d) may be used.

10.3.3 Premedication and ancillary medications for management of common symptoms related to hu14.18-IL2

Appropriate antibiotics, blood products, antiemetics, fluids, electrolytes and general supportive care are to be used as necessary.

10.3.3.1 Premedication prior to hu14.18-IL2 administration on day 1-3

Preclinical data suggest that concomitant use of indomethacin may enhance the antitumor effect of immunocytokine treatment in mice ([name], unpublished), and that indomethacin can ameliorate clinical toxicity of IL2, it is recommended that indomethacin (25 mg/dose every 6 hours) be started as a premed 1 hour before administration of hu14.18-IL2 on day 1, and continue for 12 hours after the last dose of hu14.18-IL2 during each treatment cycle. Indomethacin should not be given if renal function has worsened from baseline (> 50% increase over baseline serum creatinine) or if the platelet count is $\leq 50,000/\mu\text{l}$. Other anti-inflammatory drugs, such as ibuprofen, are permitted as a substitute for indomethacin if, in the investigator's judgment, indomethacin will not be well tolerated.

Any patient showing allergic symptoms with hu14.18-IL2 should receive diphenhydramine, acetaminophen, and an H₂ blocker (e.g., ranitidine 150 mg PO) as premedication before all subsequent doses.

Any patient experiencing pain with a dose should receive premedication with morphine (or an appropriate narcotic) before all subsequent hu 14.18-IL2 doses.

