10.2 Supportive care

10.2.1 Hematologic toxicity

All subjects will be transfused as needed to maintain an adequate Hgb level (≥ 8.0) and platelet count ($\geq 40,000$) during Days 1-3 of treatment each month. Hematologic DLT criteria are detailed in Section 5.3. As there may be an association of vascular leak syndrome with co-administration of monoclonal antibody-IL2 and transfusions, it is recommended to avoid transfusions during the 3 days of hu14.18-IL2 administration, and particularly during the daily 4-hour infusions. If transfusions are needed, it is recommended that they be given at least 12 hours before starting treatment on day 1 of each course and > 12 hours after finishing the day 3 infusion. If transfusions must be given on day 3 to maintain Hgb >8.0 and plts > 40,000, these should be given 12 hours after completing the prior 4-hr infusion of hu14.18-IL2. If the subject experiences neutropenia (ANC < 1000) while receiving the fusion protein, treatment would not be interrupted since neutropenia is common and rapidly reversible upon stopping IL2 treatment. For days 8-29 of each course of therapy, transfusions should be given, if needed, to maintain a platelet count of >20,000, and a Hgb of > 7.0.

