10.2.7 Temperature elevations

Fusion protein treatment will be held for persistent temperature elevations (> 6 hours) of 40° C or greater not responding to symptomatic treatment with antipyretics. Provided that renal function remains stable (i.e., creatinine does not increase more than 50% over baseline), all patients will receive indomethacin 25 mg/dose every 6 hours, starting 1 hour before the first dose of hu14.18-IL2 and continuing 12 hours after the last dose on day 3 (see premedication, Section 10.3.3). As most patients experience fevers, it is recommended to begin acetaminophen (325-650 mg) as soon as any elevated temperature (> 37.5° C) develops after the first dose of hu14.18-IL2, and to continue it on a scheduled basis for the next 60-72 hours (not to exceed 4 gm per day). Rigors, which may accompany temperature changes, can be treated with meperidine IV. Persistent temperature elevations > 39° C which are not well controlled with acetaminophen and indomethacin may also be treated with a cooling blanket. No dose modifications will be made for temperature elevations (unless the temperature persists > 40° C for > 6 hours) despite treatment with the above antipyretic approaches. If fever does persist for > 6 hours despite antipyretics, then hu14.18-IL2 treatment will be stopped. Treatment can be restarted within a 3-day course of treatment once the temperature is \leq 38° C. Treatment will then be at 50% of the dose which caused this toxicity.

Use of prophylactic antibiotics for fever:

Although the IL2 component of hu14.18-IL2 is known to, and expected to cause fever, IL2 is also known to cause some neutrophil dysfunction and predispose to bacterial infections, including central

catheter related infections. Thus, for fever $> 38.5^{\circ} \text{C}$, it is recommended that blood cultures be drawn, and a broad-spectrum antibiotic be considered if fever persists or the patient is clinically unstable.

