10.3.3.2 Medications acceptable for symptom management*

- Acetaminophen 650 mg PO q4 hrs PRN, fever
- Acetaminophen 325 mg/oxycodone 5 mg (Percocet) 1-2 PO q4-6 hrs PRN, pain
- Diphenhydramine 25-50 mg PO/IV q6 hrs PRN, pruritis, urticaria
- Hydroxyzine 50-100 mg PO/IM q6 hrs PRN, pruritis, urticaria or anxiety
- Dolasetron 100 mg PO/IV qd PRN, nausea/vomiting
- Granisetron 1 mg PO/IV qd PRN, nausea/vomiting
- Loperamide 2 mg tablets, 4 mg PO initially followed by 2 mg after each unformed stool; maximum of 16 mg qd PRN
- Lorazepam 0.5-1 mg PO/IV q2-4 hrs PRN, anxiety or nausea/vomiting
- Meperidine 25 mg IV q3-4 hrs PRN for chills/rigors; patients developing chills may be treated for possible infection with broad spectrum antibiotics (Section 10.2.6)
- Morphine sulfate 1-4 mg IV q2-4 hrs PRN, pain
- Naproxen 250-500 mg PO bid PRN**
- Ondansetron 24 mg IV prior to treatment/8 mg PO tid PRN, nausea/vomiting
- Oxycodone 5-10 mg PO q2-4 hrs PRN, pain
- Prochlorperazine 10 mg PO q6 hrs PRN or 25 mg PR q12 hrs PRN
- Pseudoephedrine 60 mg PO q6 hrs PRN
- Ranitidine 150 mg PO bid PRN

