***Dexamethasone and other corticosteroids MAY NOT BE GIVEN (see Section 10.3.3.4).**

**Care should be taken when using non-steroidal, anti-inflammatory drugs (NSAIDs) secondary to potential nephrotoxicity. Anti-inflammatory drugs such as naproxen are permitted.

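### The platelet limit in Section 10.3.3.1 applies to indomethacin only, so ibuprofen or as-needed naproxen stays permitted at counts where indomethacin is barred

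*Combined protocol and SAP*

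**What the plan says.** Section 10.3.3.1 recommends indomethacin from one hour before the first infusion until 12 hours after the last, and restricts it: "Indomethacin should not be given if renal function has worsened from baseline (> 50% increase over baseline serum creatinine", or when platelets are at or below 50,000/µl. The next sentence reads "Other anti-inflammatory drugs, such as ibuprofen, are permitted as a substitute for indomethacin", for subjects who in the investigator's judgment would tolerate indomethacin poorly. It attaches no limit.

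Section 10.3.3.2 separately lists "Naproxen 250-500 mg PO bid PRN". The footnote to that entry asks for care with NSAIDs because of possible nephrotoxicity, gives no threshold, does not mention platelets, and adds: "Anti-inflammatory drugs such as naproxen are permitted".

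Section 10.2.7 repeats the indomethacin order ("all patients will receive indomethacin 25 mg/dose every 6 hours, starting 1 hour before the first dose of hu14.18-IL2"). It makes the order conditional on creatinine but not on platelets, and refers the reader to Section 10.3.3. Section 10.2.10 says nephrotoxic drugs, indomethacin included, should be avoided once renal function worsens beyond twice the upper limit of normal (ULN) but short of Grade 3.

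On platelets, Section 10.2.1 aims for at least 40,000 on days 1-3. Later in the course: "For days 8-29 of each course of therapy, transfusions should be given, if needed, to maintain a platelet count of >20,000". Section 5.4.3(g) exempts Grade 3 hematologic toxicity from DLT if it is one "which improves to at least Grade 2 or pre-therapy baseline values without requiring transfusion within one week of completion of hu14.18-IL2".

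**The concern.** The plan judges 50,000/µl too low for one NSAID and gives no reason to treat the others differently. Read literally, the text lets a subject barred from indomethacin because of platelets receive ibuprofen or naproxen that day. Naproxen is the clearer case. It is an entry of its own, not a stand-in for indomethacin, and it is not confined to days 1-3.

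What is at stake is avoidable bleeding risk in an occasional subject. The setting makes that worth a sentence. Some Group A subjects may have elective biopsies around days 3-5 of course 1 (Section 7.3.2), and prophylactic-dose anticoagulation is allowed (Sections 10.3.2 and 10.3.3.4). Sample size, endpoints and analysis are not involved.

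**Working it through.** The plan states no figure to reproduce here, so the check is mainly a side-by-side reading.

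**1. Limits by drug**

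| Drug and place | Creatinine limit | Platelet limit |
|---|---|---|
| Indomethacin, 10.3.3.1 | >50% above baseline | ≤50,000/µl |
| Indomethacin, 10.2.7 | >50% above baseline | not restated; refers to 10.3.3 |
| Ibuprofen or other substitute, 10.3.3.1 | none stated | none stated |
| Naproxen as needed, 10.3.3.2 and footnote | general caution, no threshold | none stated |
| Any nephrotoxic drug, 10.2.10 | >2 × ULN, not yet Grade 3 | not addressed |

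No other section supplies a platelet limit for ibuprofen, naproxen or NSAIDs as a class.

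**2. Where the gap lies**

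- Days 1-3: indomethacin is barred at ≤50,000 and transfusion is called for below 40,000. From 40,000 to 50,000, indomethacin is barred, no transfusion is called for, and another NSAID is permitted as written.
- Days 4-7: Section 10.2.1 gives no transfusion level.
- Days 8-29: transfusion is called for at about 20,000. The indomethacin order ended 12 hours after the day-3 dose, so the question here concerns naproxen.

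**3. How long such a subject stays outside DLT**

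Hu14.18-IL2 is completed on day 3, and the Section 5.4.3(g) exemption requires recovery within one week: day 3 + 7 = day 10. A count still below 50,000 after about day 10 is a DLT. Under Section 5.4.4 a DLT stops the study agent; nothing there withdraws naproxen.

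The 50,000 boundary for Grade 3 comes from Table 3, which was graded under CTC version 2.0. The trial grades under CTCAE version 3.0 (Section 5.4.1), whose cut-offs the protocol does not reproduce, so I assume the same upper boundary. Any count that grades as 4 is a DLT in any case (Section 5.4.3).

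**4. How often**

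Entry needs platelets ≥100,000 (Section 3.1.5.1). A subject at that minimum must lose (100,000 − 50,000)/100,000 = 50% to reach the limit. Later courses need toxicity at Grade 1 or less, or initial eligibility met (Section 5.3.1).

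Table 3, platelets from 10,000 to below 50,000:

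- Course 1: denominator 3+6+6+6+6+6 = 33; 1 event, at 4.8 mg/m².
- Course 2: denominator 2+6+1+5+3+2 = 19; 0 events.
- At 6.0 mg/m²: 0 of 6 in course 1 and 0 of 3 in course 2.

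The exact (Clopper-Pearson) 95% interval for 1/33 is 0.08% to 15.8%. For 0 of 6 the exact upper limit is 1 − 0.025^(1/6) = 1 − 0.541 = 45.9%, so the absence of events at this dose says little alone. Table 3 does not say when in the course the one event occurred. I make no projection to this trial.

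**5. Renal side**

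If baseline creatinine lies between half the ULN and the ULN (my assumption), the 50% rule stops indomethacin above 1.5 × 0.5 = 0.75 to 1.5 × 1.0 = 1.5 times ULN. The class-wide rule in Section 10.2.10 starts above 2 times ULN. Between the two, other NSAIDs carry only the footnote's caution. Section 10.2.10 says of nephrotoxicity that "this has been minor in subjects receiving IL2 doses similar to those to be administered in this study", and neither the Grade 3 list in Section 1.3.5 nor Table 3 shows a renal event.

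**The case against.** The best reply is that no clinician would be misled. Ibuprofen is permitted only in place of indomethacin, directly after the limits, so the natural reading is that it inherits them. Naproxen is an optional item on a list of acceptable drugs in which no entry carries a platelet threshold, and it is one of the few with any caution. The event is rare, and the documents report no NSAID-related bleed.

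Much of this stands. The rarity is real, and the ibuprofen wording can fairly be read either way. It does not dispose of naproxen, which has its own entry and an express permission. If the limits are meant to carry over, the intended rule is class-wide and the text should say so.

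Some stronger readings are tempting but unsupported:

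- A reader might infer that an untransfused subject at 20,000-50,000 sits in a DLT-exempt gap throughout days 8-29. The exemption ends at about day 10.
- A reader might infer that Section 10.2.7 overrides the platelet limit. It refers to Section 10.3.3, where the limit stands, so the omission is one of consistency.
- A reader might fault Table 5 for not saying whether the day-3 labs are drawn before the infusion. That bears on indomethacin, whose limits are already stated, and is not part of this point.
- A reader might see an equal renal gap. Section 10.2.10 and the footnote cover most of it.

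**Conclusion.** The point holds as a minor safety-wording gap that merits a cheap correction. As written, a subject barred from indomethacin for platelets may still be given ibuprofen or naproxen. The clearest case is 40,000-50,000 on days 1-3. A lower count later in the course, whether still exempt up to about day 10 or a DLT afterwards, does not itself bar naproxen either.

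The situation should be rare: 1 of 33 in course 1 and 0 of 19 in course 2 of phase I, with none at 6.0 mg/m² on very small denominators. The conclusion rests on a literal reading of Sections 10.3.3.1 and 10.3.3.2, and on the Grade 3 platelet boundary being 50,000 under the grading version in force. It has no bearing on the statistical design.

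**What to change.** - Section 10.3.3.1, replace the indomethacin-only limit with: *No NSAID (indomethacin, ibuprofen, naproxen or other) is given if creatinine is >50% above baseline or platelets are ≤50,000/µl.*
- Section 10.3.3.2, naproxen entry, add: *subject to the limits in 10.3.3.1.*
- Optional, for consistency: add the platelet condition to the indomethacin order in Section 10.2.7.

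If only one change is made, it should be the first. The cost is wording alone, with no added blood draw or visit. A few subjects lose an NSAID option and rely on acetaminophen or opioids, both already listed in Section 10.3.3.2. The limits on indomethacin itself do not change.
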